[Part 3 of 3 of the document. The other parts are not shown.]

Throughout the study, the same DXA apparatus will be used at each site and operated in the same scan mode for all scans for an individual patient and should be the same as used for the patient during the parent study (MVT-601-3101 and MVT-601-3102). The central core imaging laboratory will collect and evaluate all DXA scan for acceptability. Bone mineral density changes for individual patients will be monitored by the central imaging laboratory over the course of the study.

Determination of bone mineral density by DXA at early termination and follow-up of findings will proceed according to the following rules:

- For early termination occurring between Week 24 and Week 52:
  - For early termination occurring before Week 36, DXA is not required at the Early Termination visit unless it will aid in the assessment of an adverse event;
    - Follow-up DXA required at 6 months ( $\pm$  1 month) if most recent DXA bone mineral density loss at lumbar spine (L1-L4) or total hip was  $> 2\%$  relative to the parent study baseline;
  - For early termination occurring after Week 36, DXA is required at early termination unless a DXA result is available from within six weeks prior to early termination;
    - Follow-up DXA is required at 6 months ( $\pm$  1 month) if the most recent DXA scan was at Week 24 and bone mineral density loss at the lumbar spine (L1-L4) or total hip was  $> 2\%$ , relative to the parent study baseline;
  - Follow-up DXA is required at 6 months ( $\pm$  1 month) if on the most recent DXA scan, bone mineral density loss at the lumbar spine (L1-L4) or total hip was  $> 3\%$ , relative to the parent study baseline;
- For early termination occurring between Week 52 and Week 104:

- DXA is required at early termination unless a DXA result is available from within six weeks prior to early termination;

Follow-up DXA is required at 6 months ( $\pm$  1 month) if on the most recent DXA, bone mineral density loss at the lumbar spine (L1-L4) or total hip was  $> 7\%$ , relative to the parent study baseline;

- If patients have 6-month post-treatment follow-up scans that show bone loss of  $> 1.5\%$  at the lumbar spine and/or  $> 2.5\%$  at total hip compared with parent study baseline, patients are strongly encouraged to come back to the clinic for an additional post-treatment follow-up scan 12 months from the date of the last dose of the study drug. Patients undergoing 6-month post-treatment follow-up should also have the following clinical laboratory evaluations (vitamin D, thyroid-stimulating hormone, parathyroid hormone, creatinine, calcium, and phosphorous).
- If patients have 12-month post-treatment follow-up scans that show bone loss of  $\geq 3\%$  at the lumbar spine and/or total hip compared with parent study baseline, patients are referred to and strongly encouraged to see a bone specialist for further evaluation or the bone loss. Patients undergoing 12-month post-treatment follow-up should also have the following clinical laboratory evaluations (vitamin D, thyroid-stimulating hormone, parathyroid hormone, creatinine, calcium, and phosphorous).

Note: When a patient is referred to a bone specialist for evaluation and management, Myovant will provide a Bone Consultation Letter to the investigator for this additional bone consult and will request the site to provide a summary of the evaluation and management plan once the consultation is complete.

#### **6.5.2.7. Endometrial Biopsy**

For patients in parent study MVT-601-3101, an endometrial biopsy is performed at the Week 24 visit. If the required Week 24 biopsy is inadequate for diagnosis, it should be repeated, and a sample submitted to the central laboratory. If the second sample is inadequate, ensure an endometrial thickness has been reported from the Week 24 transvaginal ultrasound and contact the medical monitor to review the findings. Patients who have endometrial hyperplasia or endometrial carcinoma will be withdrawn from study drug treatment and followed per instructions in the parent study protocol.

Additional assessment of the effects of relugolix co-administered with low-dose estradiol and norethindrone acetate on the endometrium will be performed at Week 52 and Early Termination visit for all patients. An endometrial biopsy is required for all patients at the Early Termination visit except for patients whose last dose of study drug was taken during Week 32 or earlier or within four weeks after completion of the Week 52 endometrial biopsy. However, the endometrial biopsy may be obtained if it will aid in the evaluation of an ongoing adverse event. An endometrial biopsy at Week 104 is recommended for all patients who complete the open-label extension; however, patients will have the option to opt out. Patient participation in the Week 104 endometrial biopsy is voluntary and refusal to participate will not preclude entry into the study or indicate withdrawal from the study.

The Week 52, Week 104, and Early Termination visit endometrial biopsy samples will be submitted to the central laboratory. If the Week 52, Week 104, or Early Termination visit biopsy

specimen is inadequate, a transvaginal ultrasound for endometrial thickness should be obtained and read locally. The transvaginal ultrasound findings will be used to determine if further action is required:

- Endometrial thickness  $\leq 5$  mm – no further action required.
- Endometrial thickness  $> 5$  mm at any location or any other endometrial abnormality – repeat endometrial sampling. Contact medical monitor if second specimen is inadequate for diagnosis.

Investigators should contact the medical monitor if a patient refuses to have an endometrial biopsy at Week 52 or the Early Termination visit. Unscheduled endometrial biopsies may also be performed when medically indicated and as deemed necessary by the investigator. The investigator should obtain approval from the sponsor to perform an unscheduled endometrial biopsy, unless urgently indicated. Additional consent is not required in this circumstance.

#### **6.5.2.8. Status of Menstruation Recovery**

If the first menstruation after the end of study treatment administration is observed before the Follow-up visit, the date of onset of the first menstruation is recorded in the eCRF. Patients whose menses has not resumed as of the Follow-Up visit for whom there is no explanation for the lack of resumption (eg, medical procedure or medications) will be contacted by telephone 3 (+0.5) months after the Follow-Up visit to determine if menses has resumed and will be asked about factors that may affect resumption of menses. If a patient is lost to follow-up, three documented attempts should be made to contact the patient by telephone. If unable to contact the patient by telephone, a certified letter must be sent to the patient.

If the patient enrolls directly into another relugolix clinical study upon completion of the Week 104 visit, follow-up under this protocol to determine the status of menstruation recovery may not be required.

#### **6.5.2.9. Mammogram**

A mammogram will be performed at Week 52 or Week 104/Early Termination visit (see the Schedule of Activities in Section 1.1) for patients  $\geq 40$  years of age at the time of the visit. If a patient had a recent mammogram per standard of care within the six months before Week 52 that was Breast Imaging Reporting and Data System category 1 or 2 or equivalent or had benign findings, as determined by the investigator or medical monitor, a mammogram is not required at Week 52 but should be completed by Week 104/Early Termination. If a patient turns 40 years old after the Week 52 visit has occurred, a mammogram should be performed no later than the Week 104/Early Termination visit.

All mammogram results will be read locally using Breast Imaging Reporting and Data System categories or equivalent (see [Appendix 8](#)) and recorded in the eCRF. The following actions will be taken depending on the reading:

- Category 1 or 2 or equivalent: normal mammogram; no further action is required unless determined by the investigator or medical monitor;

- Category 0 or 3 or equivalent: adjunctive breast imaging or follow-up mammogram will be required, and the investigator should contact the medical monitor for approval of additional breast imaging;
- Category 4 to 6 or equivalent: the investigator should contact the medical monitor within 24 hours.

---

## 7. SAFETY CONSIDERATIONS

Study assessments of safety include adverse events, vital signs and weight, physical examinations, clinical laboratory tests, ECGs, and bone mineral density assessments.

### 7.1. Adverse Event Definitions

#### 7.1.1. Adverse Event

Adverse event: An adverse event is any unfavorable and unintended sign (including an abnormal laboratory finding), symptom, or disease (new or exacerbated) temporally associated with the use of a medicinal product, whether or not related to the medicinal product.

Events meeting the definition of an adverse event **include**:

- A worsening, excluding minor fluctuations, in the nature, severity, frequency, or duration of a pre-existing condition;
- Development of an intercurrent illness during the study;
- Development of symptoms that may or may not be related to the use of a concomitant medication or investigational product;
- Injury or accidents: If a medical condition is known to have caused the injury or accident, the medical condition and the accident should be reported as 2 separate medical events (eg, for a fall secondary to dizziness, both “dizziness” and “fall” should be recorded separately); and
- An investigational abnormality (eg, laboratory parameter, vital sign, ECG) only if the abnormality is considered clinically significant by the investigator based on at least one of the following criteria:
  - Induces clinical signs or symptoms;
  - Requires active intervention;
  - Requires interruption or discontinuation of study drug.

Events that **do not** meet the definition of an adverse event include:

- Medical or surgical procedures (eg, surgery, endoscopy, tooth extraction, transfusion); the condition that leads to the procedure is an adverse event;
- Pre-existing diseases or conditions present or detected before the start of study drug administration that do not worsen;
- Situations where an untoward medical event has not occurred (eg, planned hospitalization for an elective procedure, with elective defined as known or planned at the time of signing of the informed consent);
- Endometriosis-associated pain is not considered an adverse event in this study because it is being quantitatively measured as the primary efficacy endpoint.

Adverse events that occur during the study should be evaluated by the investigator and graded according to the National Cancer Institute Common Terminology Criteria for Adverse Events

(CTCAE). Episodic adverse events, such as vomiting, or those that occur repeatedly over a period of consecutive days are “intermittent”. All other events are “continuous”. Additional information on detecting, documenting, and reporting adverse events and serious adverse events are provided below.

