## 7.5. Adverse Events of Clinical Interest Reporting

Adverse events of clinical interest in this study are defined as any increase in ALT or AST  $\geq 3 \times$  ULN.

Any ALT or AST elevation of this degree or greater occurring during the Open-Label Treatment Period or the Follow-Up visit should be reported to the sponsor using the Safety Report Form **within 24 hours of the study site personnel's knowledge of the event** (see Section 7.6), **even if the event does not meet serious adverse event criteria**. Additional instructions for evaluating patients with an increase in ALT or AST  $\geq 3 \times$  ULN may be found in [Appendix 7](#).

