**Table 6-1 Clinical Laboratory Tests**

Chemistry	Hematology	Urinalysis
Potassium	White blood cell count	Protein
Chloride	White blood cell differential	Glucose
Bicarbonate	Red blood cell count	Blood
Blood urea nitrogen	Hemoglobin	Urobilinogen
Creatinine	Hematocrit	Bilirubin
Glucose	Mean corpuscular volume	Color and clarity
Calcium	Platelet count	pH
Phosphate	Red blood cell morphology	Leucocyte esterase
Magnesium		Ketones
Sodium		Nitrite
Albumin		Specific gravity
Creatine kinase		Urine microscopy (reflex testing based on abnormal urine analysis)
Hemoglobin A1c		
Bilirubin total		
Alanine aminotransferase		
Aspartate aminotransferase		
Gamma-glutamyl transferase		
Alkaline phosphatase		
Hormones	Lipids	Pregnancy
Estradiol	Total cholesterol	Pregnancy test (human chorionic gonadotropin)
	Low-density lipoprotein	
	High-density lipoprotein	
	Triglycerides	

The central laboratory will perform laboratory tests for chemistry, hematology, urinalysis, and serum hormone levels. Each study site will conduct urine pregnancy tests locally.

All laboratory tests with values that are considered abnormal and clinically significant during participation in the study or within 30 days after the last dose of study drug should be repeated until the values return to normal, baseline, or have stabilized. Abnormal values, determined to be clinically significant, should be reported as adverse events.

For patients with incomplete recovery of bone mineral density loss at the 6- and 12-month post-treatment follow-up visit, clinical laboratory tests should be performed (see Section 6.5.2.6). These laboratory assessments will be submitted to the central laboratory. If these laboratory assessments are scheduled to occur after the study database is locked, they will be performed at a local laboratory. The investigator will maintain a copy of the reference ranges (with the record of the reference ranges) for the laboratory or laboratories used.

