### 7.1. Adverse Event Definitions

#### 7.1.1. Adverse Event

Adverse event: An adverse event is any unfavorable and unintended sign (including an abnormal laboratory finding), symptom, or disease (new or exacerbated) temporally associated with the use of a medicinal product, whether or not related to the medicinal product.

Events meeting the definition of an adverse event **include**:

- A worsening, excluding minor fluctuations, in the nature, severity, frequency, or duration of a pre-existing condition;
- Development of an intercurrent illness during the study;
- Development of symptoms that may or may not be related to the use of a concomitant medication or investigational product;
- Injury or accidents: If a medical condition is known to have caused the injury or accident, the medical condition and the accident should be reported as 2 separate medical events (eg, for a fall secondary to dizziness, both “dizziness” and “fall” should be recorded separately); and
- An investigational abnormality (eg, laboratory parameter, vital sign, ECG) only if the abnormality is considered clinically significant by the investigator based on at least one of the following criteria:
  - Induces clinical signs or symptoms;
  - Requires active intervention;
  - Requires interruption or discontinuation of study drug.

Events that **do not** meet the definition of an adverse event include:

- Medical or surgical procedures (eg, surgery, endoscopy, tooth extraction, transfusion); the condition that leads to the procedure is an adverse event;
- Pre-existing diseases or conditions present or detected before the start of study drug administration that do not worsen;
- Situations where an untoward medical event has not occurred (eg, planned hospitalization for an elective procedure, with elective defined as known or planned at the time of signing of the informed consent);
- Endometriosis-associated pain is not considered an adverse event in this study because it is being quantitatively measured as the primary efficacy endpoint.

Adverse events that occur during the study should be evaluated by the investigator and graded according to the National Cancer Institute Common Terminology Criteria for Adverse Events

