## 7.5. Adverse Events of Clinical Interest Reporting

Adverse events of clinical interest in this study are defined as any increase in ALT or AST  $\geq 3 \times$  ULN.

Any ALT or AST elevation of this degree or greater occurring during the Open-Label Treatment Period or the Follow-Up visit should be reported to the sponsor using the Safety Report Form **within 24 hours of the study site personnel's knowledge of the event** (see Section 7.6), **even if the event does not meet serious adverse event criteria**. Additional instructions for evaluating patients with an increase in ALT or AST  $\geq 3 \times$  ULN may be found in [Appendix 7](#).

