**Table 7-2 Protocol Risk Assessment and Mitigation Strategies**

Potential Risk of Clinical Significance	Mitigation Strategy	
	Impact on Eligibility	Monitoring and Withdrawal Criteria
Bone Mineral Density Reversible loss of bone mineral density is a risk of the hypoestrogenic state induced by relugolix. This risk is mitigated by the co-administration of low-dose estradiol and norethindrone acetate hormonal add-back therapy.	Exclusion criteria for a history of osteoporosis, metabolic bone disease, and prior medical therapy for low bone mineral density was included in the parent studies.	Bone mineral density will be monitored at the Week 24/Baseline, Week 36, Week 52, and Week 104/Early Termination visits with specified discontinuation and follow-up criteria and all fractures will be reported as adverse events.
Drug Interactions	Exclusion of co-administration P-glycoprotein inhibitors/inducers.	Collection of adverse events.

Potential Risk of Clinical Significance	Mitigation Strategy	
	Impact on Eligibility	Monitoring and Withdrawal Criteria

QTc Prolongation
 
Negative Thorough QT/QTc clinical study.
	
Empiric exclusion of baseline QTcF > 470 msec in the parent studies.
	
12-lead ECG at the Week 24/Baseline and Week 52 visits, and as clinically applicable; withdrawal for QTcF > 500 msec.

Hepatic Enzymes
 
Isolated increases in hepatic transaminases have been observed in prior clinical studies. There have been no reported cases consistent with drug-induced liver injury including an increase in bilirubin. Abnormal liver test results are considered adverse events of clinical interest in this study.
	
Exclusion criteria for AST and ALT > 2 × the ULN; total bilirubin values > 1.5 × ULN.
	
Abnormal liver test results (AST or ALT > 3 × ULN) that develop during the Open-Label Treatment Period will be reported within 24 hours of study personnel awareness.

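### Sections 7.1.1 and 7.5 disagree on whether a symptom-free, untreated ALT/AST rise of at least 3 × ULN that does not interrupt study drug is an adverse event, and neither is said to prevail

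*Protocol*

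**What the plan says.** The text at issue is that of Amendment 3.1; the Amendment 3 copy in the same file carries the same wording in Sections 7.1.1 and 7.5.

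- **Section 7.1.1** opens broadly, defining an adverse event as "any unfavorable and unintended sign (including an abnormal laboratory finding" among other things. Its list of qualifying events then narrows this for laboratory values: "An investigational abnormality (eg, laboratory parameter, vital sign, ECG) only if the abnormality is considered clinically significant by the investigator", judged on at least one of three criteria. The first is that the abnormality produces signs or symptoms, the second that it needs active intervention, and the third reads "Requires interruption or discontinuation of study drug".
- **Section 6.5.2.4**, below Table 6-1, repeats the significance condition: "Abnormal values, determined to be clinically significant, should be reported as adverse events".
- **Section 7.5** has no such condition: "Adverse events of clinical interest in this study are defined as any increase in ALT or AST" to at least 3 × ULN. Such a rise, during open-label treatment or at the Follow-Up visit, "should be reported to the sponsor using the Safety Report Form" within 24 hours, "even if the event does not meet serious adverse event criteria".
- **Table 7-2**, hepatic row, also classes abnormal liver tests as adverse events of clinical interest. It sets the threshold at more than 3 × ULN and refers to results "that develop during the Open-Label Treatment Period will be reported within 24 hours of study personnel awareness", without the Follow-Up visit.
- **Section 7.2** requires every adverse event to be entered on the adverse event case report form.
- **Section 9.5** tabulates adverse event incidence by system organ class and preferred term. It separately gives CTCAE-grade shift tables from central-laboratory data.

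**The concern.** For a transaminase rise that is symptom-free, untreated and does not interrupt dosing, 7.1.1 and 6.5.2.4 say it is not an adverse event and 7.5 says it is. Section 7.5 sets aside only the seriousness criteria, not the three criteria of 7.1.1, and the only form it names is the Safety Report Form. A site that applies 7.1.1 literally could send that form and enter nothing on the adverse event eCRF, while a site that applies 7.5 would enter an event for the same value.

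Incidence of adverse events is a named safety endpoint at Week 52 and Week 104. Table 7-2 reports that isolated transaminase increases were seen in prior studies, so the ambiguity falls on an expected hepatic finding. What is at stake is consistent counting of the liver-enzyme preferred terms across sites.

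**Working it through.** The plan states no figure on this point, so there is nothing to reproduce. The check sets the withholding rules (7.5.1 and Appendix 7) beside the two definitions, to find which rises satisfy 7.5 but not 7.1.1.

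| ALT or AST rise | Drug withheld? | Adverse event under 7.1.1? | Under 7.5? |
|---|---|---|---|
| Above 8 × ULN | Yes, 7.5.1 | Yes, third criterion | Yes |
| Above 5 × ULN for more than 2 weeks | Yes, 7.5.1 | Yes, third criterion | Yes |
| Above 3 × ULN with bilirubin > 2 × ULN or INR > 1.5 | Yes, 7.5.1 | Yes, third criterion | Yes |
| Above 3 × ULN with a listed symptom, or eosinophilia > 5% | Yes, 7.5.1 | Yes, third criterion | Yes |
| At least 3 × ULN, none of the above, close monitoring not possible | Yes, Appendix 7 | Yes, third criterion | Yes |
| At least 3 × ULN, none of the above, but actively treated | No | Yes, second criterion | Yes |
| At least 3 × ULN, none of the above | No | **No** | **Yes** |

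Only the last row is in conflict. It covers values from 3 to 5 × ULN of any duration, and values above 5 and up to 8 × ULN lasting no more than 2 weeks. Bilirubin is at most 2 × ULN and INR at most 1.5, and there are no signs or symptoms, no eosinophilia above 5% and no active intervention. Rises that meet 7.5.1 are also to be reported as serious adverse events, so they are not in doubt.

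Two features make the boundary depend on the site:

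1. Appendix 7 withholds drug when close monitoring is not possible. The same value can therefore meet the third criterion at one site and not at another.
2. *Active intervention* is not defined. Appendix Table 1 asks for repeat tests every 48 to 72 hours when an isolated rise reaches 3 × ULN, and Appendix Table 2 recommends serologies and imaging. One investigator may count this work-up as intervention and another may not.

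**Size.** The documents give no rate for the last row. As an illustration on an assumed 0.5% to 2% of the planned 800 or so women:

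- 0.005 × 800 = 4 women;
- 0.02 × 800 = 16 women.

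Overall adverse event incidence would then differ by at most 0.5 to 2 percentage points between all sites applying 7.5 and all sites applying 7.1.1. The difference is smaller to the extent that these women have another adverse event. It would fall mainly on the liver-enzyme preferred terms.

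**Table 7-2 against 7.5.** The difference between more than and at least 3 × ULN matters only for a value of exactly 3 × ULN. The difference in period is wider, because a rise found at the Follow-Up visit is covered by 7.5 and not by the table.

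**The case against.** The strongest reply is that the protocol already reaches the right answer. Section 7.5 is the specific rule, it calls these rises adverse events, Table 7-2 agrees, and Section 7.2 sends all adverse events to the case report form. On that reading an event is omitted only where a site puts the general rule above the specific one. This is a fair reading and probably the intended one. It does not close the gap: 7.2 applies once something is an adverse event, which is the question on which 7.1.1 and 7.5 differ, and no sentence gives precedence.

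A reader might infer that isolated liver elevations as a class drop out of the endpoint, or that a hepatic signal would be lost. The documents do not support either. Isolated rises above 8 × ULN, or above 5 × ULN for more than 2 weeks, qualify under both rules. Central-laboratory rises appear in the shift tables and by-visit summaries however the event is coded. The exception is local draws under the COVID-19 guidance in Appendix 9. Those results are entered in the eCRF, but Section 9.5 keeps them out of the laboratory analyses.

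A reader might also infer that the safety and clinical databases will disagree. That cannot be concluded, because the protocol refers to case report form completion guidelines that are not shown and commits to cleaning inconsistent data. Finally, the analyses are descriptive with no formal treatment comparison, so no test result depends on this. These points limit the consequence; the contradiction in the text remains.

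**Conclusion.** The inconsistency is real and narrow. Two operative rules classify the same laboratory value in opposite ways for a named safety endpoint, and the protocol does not say which governs. The result is possible site-to-site variation in recording; an understated hepatic incidence is not established. The affected rises are those in the last row of the table above, and their number is unknown: 4 to 16 women rests wholly on the assumed 0.5% to 2%. The conclusion assumes only that some sites may apply 7.1.1 and 6.5.2.4 as written. The mismatch between Table 7-2 and 7.5 is a lesser wording fault of the same kind.

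**What to change.** - In Section 7.1.1, and in the matching sentence of 6.5.2.4, state that any event meeting the Section 7.5 definition is recorded on the adverse event eCRF whether or not one of the three significance criteria is met.
- Reconcile the hepatic row of Table 7-2 with Section 7.5, so that one threshold and one reporting period are stated in both places.

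This is a recording rule and leaves the withholding and discontinuation criteria untouched. Section 9.5 needs no change: matching Safety Report Forms to the eCRF can stay with the data-management documents. The cost is one sentence in each of two sections and one table cell. The reported count of liver-enzyme adverse events may rise slightly where sites have been applying 7.1.1.
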